1. Potential subjects will see Drs. [name], [name], [name], [name] or [name] at their visit prior to elective anterior cervical spine surgery at the Spine or Neurosurgery Clinic. 2. Subjects will be told about the study at this visit, all questions will be answered by the surgeons and the research coordinator, all surveys that need to be completed will be shown to the potential subjects and they will be given the opportunity to consent. 3. If consented, the subject will be asked to complete baseline surveys (Bazaz, EAT-10, and Dysphagia Short Questionnaire) at this visit. The subject will also complete Standard of Care Patient Reported Outcome Measures (PROMS) at this visit. 4. The subject will be randomized to receive either single dose steroid (dexamethasone) or saline (placebo) prior to surgery. The dose is calculated based on body weight group will receive 0.3 mg/kg of intravenous dexamethasone (experimental group) 0.3 mg/kg saline (control group). The subject will not be charged for dexamethasone or saline. 5. The subject will undergo anterior cervical spine surgery per standard of care. 6. After administration of the antibiotics in the operating room, the single dose of steroid or saline will be given by the anesthesia team, who are blinded to the group assignment, via an intravenous bag (study drug) prepared by the investigational pharmacist, the only person who knows the group assignment. 7. The surgeon, patient, and research team are blinded to the group assignment. 8. The subject will be administered the surveys by phone call or in the hospital by the research coordinator on Day 1. 9. On Day 2, if the subject is still hospitalized, surveys will be administered by the research coordinator in the hospital or via phone call. 10. Following Day one surveys, and if the subject has been discharged, the subject will be called to complete the answers to the surveys via phone call at Day 2, Week 1, Week 2, Month 1, Month 3, Month 6 and Month 12. At Month 12, the subject will be asked to also complete standard of care PROMS. If the subject is in the clinic for follow up at the designated time frame for survey administration, the surveys will be completed in the clinic. If the subject is not in clinic at Month 12, the PROMS will be completed via phone call. 10. At the end of the study, all subjects will be called or mailed a letter indicating the group assignment they had been in. 11. Study Results will not be shared with the subjects.

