Please describe the investigational procedures that will be performed throughout the duration of the study.

Randomization to steroids or no steroids for anterior spinal fusion subjects and completion of the Bazaz, Short Dysphagia Questionnaire and EAT-10 survey.

Please describe the standard of care procedures that will be performed throughout the duration of the study.

Everything outside of the randomization.

Will you be assigning or randomizing participants to groups or conditions (e.g., control, placebo)?

Yes

Describe the group assignment.

Random assignment to receive either one dose of steroid or one dose of saline (Placebo) during the first hour of surgery.

Does the research involve surveys/interviews/questionnaires? If so, attach a copy of the interview/survey questions on the Notes & Attachments page.

Yes

Will you be asking any questions that are likely to distress your subjects (e.g., questions about abuse, trauma, or suicide ideation)? If so, attach counseling services referral list on the Notes & Attachments page.

No

Describe what is known about this topic and why this study is needed. Please include at least two reference citations to support your rationale.  
See lit review and scientific rationale under Notes and Attachments.

What method are you going to use to analyze the data?

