Swallowing symptoms will be measured using the patient reported Bazaz Dysphagia Scale, EAT-10 survey, and the Dysphagia Short Questionnaire. Swallowing data will be obtained pre-operatively, one and two days post-operatively and then one week, two weeks, four weeks, three months, six months, and one year post-operatively. Scores from the Bazaz Dysphagia Scale and the Dysphagia Short Questionnaire from the two groups will be compared at the various time points using the Mann-Whitney U test. Power and sample size calculations are based on the presence or absence of dysphagia at two weeks. Based on a literature review, we postulated that 50% of the patients in the control group would experience mild, moderate, or severe dysphagia. If that figure can be improved to the point where just 20% of the patients are similarly affected then that, in our opinion, would represent clinical success. Under the above scenario, 32 patients in each group would give us 81% power to reject the null hypothesis. Assuming a dropout rate of 20% our total sample size for the study is 80. Statistical significance is set at  $p < 0.05$ . We plan to analyze the data in three ways. First, we will look at the time-to-event where the event is "no dysphagia" in a discrete time survival model. Second, we will use a repeated measures ordinal categorical model to assess the effect of steroid/control in a generalized linear model. Lastly, we will compare the data from this study with that of our previous three-dose model to assess any difference in the degree of impact of the two dosing regimens.

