### Subjects

Indicate the maximum number of subjects to be enrolled or medical records to be reviewed at all sites by the WVU or VAMC research team.

80

Provide a rationale for choosing your sample size.

Scores from the Bazaz scale, the EAT-10, and the Dysphagia Short Questionnaire from the two groups will be compared at the various time points using the Mann-Whitney U test. Statistical significance is set at  $p<0.05$ . With a power of 0.80 and a clinical meaningful difference of 30% in scores, an estimated 32 patients per group is needed. However, based on a recent unpublished study at our institution, we expect a dropout rate of approximately 20%, and therefore plan for a total sample size for this study of 80 patients.

State the requirement(s) to become a participant in the study (e.g., age range, sex, language spoken, class enrollment/ranking).

Ages 18-80; undergoing elective ACDF, hybrid constructs, corpectomies, disc arthroplasty surgery

Explain why selection of participants will be equitable addressing gender, ethnicity, and/or race of subjects.

No one will be excluded based on gender, ethnicity or race. Exclusion criteria include: < 18 years of age; major trauma or neoplastic or infectious conditions requiring surgery. Also excluded will be patients undergoing anterior-posterior operations, those with a history of previous anterior cervical spine surgery, any patient requiring a halo vest, patients on chronic steroids, and patients remaining intubated post-operatively, and women who are pregnant.

In outline format and chronological order, describe what will be done to identify and recruit participants (e.g., A, B, C or 1, 2, 3).

1. Potential subjects will see Drs. [name], [name], [name], [name] or [name] at their History and Physical visit prior to elective anterior cervical spine surgery at the Spine Center. 2. Subjects will be told about the study at this visit, all questions will be answered by the surgeons and the research coordinator, all surveys that need to be completed will be shown to the potential subjects and they will be given the opportunity to consent. 3. If consented, the subject will be asked to complete baseline surveys (Bazaz, EAT-10 and Dysphagia Short Questionnaire) at this visit. 4. The subject will be randomized to receive either single dose steroid (dexamethasone) or saline (placebo) prior to surgery.

Will any of the subjects be less than 18 years old?

No

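### Remaining intubated after surgery is listed as an exclusion, but it can be known only after randomisation and dosing, and nothing visible says how these patients are followed or analysed

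*Combined protocol and SAP*

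**What the plan says.** The exclusions appear in the Subjects section, in the answer on equitable selection. Among them are "patients on chronic steroids, and patients remaining intubated post-operatively". Most of the other items, such as age, pregnancy, chronic steroid use and previous anterior cervical surgery, are settled before the operation.

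The order of events is in the Design section. Allocation is at step 4 of the procedures: "The subject will be randomized to receive either single dose steroid (dexamethasone) or saline (placebo) prior to surgery". The operation is step 5. Dosing is step 6: "After administration of the antibiotics in the operating room, the single dose of steroid or saline will be given by the anesthesia team". The group-assignment answer in the same section puts it this way: "Random assignment to receive either one dose of steroid or one dose of saline (Placebo) during the first hour of surgery".

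Follow-up begins the next day: "The subject will be administered the surveys by phone call or in the hospital by the research coordinator on Day 1". Surveys then continue at Day 2, Weeks 1 and 2, and Months 1, 3, 6 and 12. On the sample size, the analysis answer says: "Power and sample size calculations are based on the presence or absence of dysphagia at two weeks". It allows for 20% dropout and arrives at 80 patients, which the Subjects section also gives as the enrolment maximum.

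No visible text names an analysis population or gives a missing-data rule. Nor does it say whether a patient who stays intubated is withdrawn, replaced, surveyed later or counted within the 20% dropout.

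**The concern.** An eligibility criterion should be decidable before allocation. This one depends on the patient's state at the end of surgery, after the study drug has been given, so it cannot screen anyone out before randomisation. It can only remove patients who have already consented, been randomised and been treated.

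Two things are at stake. First, the groups compared would no longer be the groups as randomised. If staying intubated is related to treatment or to later dysphagia, the comparison can be biased in either direction. Second, excluding these patients would give up surveys that could still be obtained. Someone who cannot answer on Day 1 or 2 may well be able to answer at two weeks, the visit on which the power calculation rests, and at later visits up to Month 12.

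**Working it through.** **Timing**

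| Step | Event | Source |
|---|---|---|
| 1 | Consent and baseline surveys | Design, procedures 2–3; Subjects |
| 2 | Randomisation, before surgery | Design, procedure 4; Subjects |
| 3 | Study drug given in the operating room, first hour of surgery | Design, procedure 6 and group assignment |
| 4 | Surgery ends; intubation status is known | follows from the criterion itself |
| 5 | Day 1 survey, then visits to Month 12 | Design, procedures 8–10 |

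The criterion is settled at step 4, after steps 2 and 3. If the words about timing in procedure 4 are taken to describe the dose and not the allocation, the order does not change: intubation status still comes after both.

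**The plan's own sample size**

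32 per group × 2 = 64 evaluable, and 64 / (1 − 0.20) = 80. This reproduces the stated total. It contains no separate allowance for exclusions after randomisation.

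**Effect on the estimate**

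The documents give no intubation rate, so what follows is an illustration. Inputs:

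- 40 randomised per arm (80 / 2).
- Two-week dysphagia of 50% on control and 20% on steroid (Design, analysis answer), that is 20/40 and 8/40.
- *k* patients excluded from one arm, all of whom would have had dysphagia at two weeks (assumed).

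With everyone kept, the difference is 20/40 − 8/40 = 30.0 points.

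| Scenario | Formula | k = 1 | k = 2 | k = 3 |
|---|---|---|---|---|
| Control patients removed | (20 − k)/(40 − k) − 0.20 | 28.7 | 27.4 | 25.9 |
| Steroid patients removed | 0.50 − (8 − k)/(40 − k) | 32.1 | 34.2 | 36.5 |
| No true effect (50% in both arms), steroid patients removed | 0.50 − (20 − k)/(40 − k) | 1.3 | 2.6 | 4.1 |

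Milder cases:

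- Two removed from each arm, all with dysphagia: 18/38 − 6/38 = 31.6 points.
- Two control patients removed, one with dysphagia: 19/38 − 0.20 = 30.0 points.
- Two steroid patients removed, one with dysphagia: 0.50 − 7/38 = 31.6 points.

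**Effect on power**

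Suppose a share *q* of each arm is excluded on top of 20% dropout. Evaluable n per arm is then 40 × (1 − q) × 0.8. Two-sided power at 0.05 for 50% versus 20% (pooled normal approximation) is:

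| q (assumed) | n per arm | Power | Total needed to keep 64: 64 / [0.8(1 − q)] |
|---|---|---|---|
| 0 | 32.0 | 72.1% | 80 |
| 1% | 31.7 | 71.6% | 81 |
| 2% | 31.4 | 71.2% | 82 |
| 5% | 30.4 | 69.8% | 85 |
| 10% | 28.8 | 67.4% | 89 |

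The plan states 81% power at 32 per group. The same approximation gives 72.1% two-sided and 82.1% one-sided, and the plan does not state sidedness. That is a separate matter and does not bear on this point. The loss of power is small if few patients stay intubated, so the main issue is how these patients are handled.

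**The case against.** The strongest case on the other side has five parts.

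- **The item could mean patients expected to stay intubated.** The list answers an ethics-board question, and neighbouring items such as needing a halo vest or a combined anterior-posterior operation describe perioperative plans. But the text speaks of patients who remain intubated, not of those expected to. If the narrower meaning was intended, the words need changing anyway.
- **Nothing says that the surveys stop.** True: loss of the later data is an inference from the word exclusion. It is the ordinary consequence of excluding someone, and no visible rule says otherwise.
- **The numbers may be tiny.** Surgery is elective, and trauma, tumour, infection and previous anterior surgery are excluded. The largest shifts need one-sided losses, all with dysphagia. The standard error of the difference at 40 per arm is √[(0.25 + 0.16)/40], or about 10.1 points, and every illustrated shift is smaller than that. The illustration also concerns the two-week proportions used for power, not the Mann-Whitney tests or the survival and ordinal models. All of this stands, and it limits the severity.
- **The trial is blinded.** Surgeon, patient, anesthesia team and research team do not know the allocation, which makes selective exclusion by arm unlikely. It does not help if the drug itself affects who stays intubated. The documents neither state nor rule out such a link.
- **A rule may exist elsewhere.** Several attachments and some pages are not shown. The finding is therefore limited to the visible text, where the exclusion itself appears.

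**Conclusion.** The concern holds. The timing follows directly from the Design and Subjects sections: the criterion can be applied only after allocation and dosing. It is a stated rule, not just a missing detail, and nothing visible keeps these patients in the follow-up or the analysis.

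The consequence is much less certain than the timing. Under the stated assumptions, losing one to three patients from one arm moves a 30-point difference to anywhere between 25.9 and 36.5 points, or creates up to 4.1 points of apparent benefit where none exists. If the excluded patients are few, balanced across arms or no more prone to dysphagia than others, the effect may be negligible. If nobody stays intubated it is nil. The documents supply neither a rate nor a link to treatment or outcome, so neither size nor direction can be fixed. This should be corrected, ideally before unblinding so that the handling cannot be influenced by results, but it does not by itself undermine the trial.

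**What to change.** 1. Delete the phrase on remaining intubated from the exclusion criteria in the Subjects section.
2. State that every randomised patient is followed through all visits to Month 12 and analysed in the group to which they were randomised.
3. In the main analysis, treat Bazaz, EAT-10 and Dysphagia Short Questionnaire surveys that cannot be obtained because of intubation as missing, under a rule written down in advance. These should fall mainly on Days 1 and 2.
4. As a sensitivity analysis, assign the worst category or score on all three instruments at those visits. This tests the early visits only; the two-week comparison is protected by item 2.
5. Report the number remaining intubated by arm.

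The cost is one line of eligibility text, one analysis-set sentence and one missing-data rule. The downside is a few missing early surveys and one extra sensitivity analysis. The change itself needs no additional patients.

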### Consent Procedures

Will SIGNED informed consent be obtained from subjects (all or in part)?

Yes

Will the informed consent form be translated into any other language(s)?

No

Is a waiver of informed consent being requested (i.e., there will be no consent process at all)?

No

Is a waiver of the requirement to obtain written documentation of the consent process being requested (if yes, attach the information to be provided to the participants)?

No

Are you requesting an alteration of consent (e.g., short form, braille consent or witnessed verbal consent)?

No

Describe the consent process (using 1, 2, 3 or A, B, C), addressing when, where, and how participants will be informed.

Potential participants will be told of the study in the Spine or Neurosurgery Clinic in a private room during their History and Physical visit prior to surgery. A research team member will inform the subject about the study, answer all their questions, show them the surveys and the subject will be given the opportunity to consent.

Indicate who will be consenting subjects and describe the process of training all personnel who will be obtaining consent.

Research team members including research coordinators who have been consenting patients for years.

### **Potential Benefits**

Is there any known benefit to the individual subject as a result of participating in the research? Payments to subjects should not be included in this section, but addressed in the Payments/Reimbursements section.

Potential benefit is less difficulty swallowing if the subject is assigned to the steroid group.

Describe the potential benefit(s) to society and/or scientific / medical knowledge of the planned work.

The results of this study will provide evidence for the use of steroids as a treatment for reducing the incidence and severity of dysphagia among patients undergoing anterior cervical spine surgery. A recently performed study at our institution has promising results from a three-dose regimen of steroids.

Similarly, two recent clinical studies have also shown decreased dysphagia with a multi-dose steroid regimen. If the hypothesis of this proposal is supported, the use of a single dose of perioperative steroid specifically lends itself well to application in patients undergoing these procedures in outpatient surgery centers, improving the safety of such procedures.

### **Confidentiality**

At any point during this study, will identifiable data be viewed or recorded?

Yes

Data must be kept for a minimum of three (3) years after study completion. In addition to the required 3 years, how much longer will the data be kept?  
Three years after study completion.

Where will data be securely located?

In REDCAP, on the password protected computer of a research team member in the Department of Orthopaedics.

How will data be destroyed?

It will be erased from the password protected computer.

Will anyone other than the PI, research team members, or IRB have access to the identifiable data (e.g., sponsor/funding source, other collaborators)?  
No

Describe the steps that will be taken to maintain the privacy of subjects (e.g., where interaction takes place) and the confidentiality of data (e.g., master code).

1. Potential subjects will see Drs. [name], [name], [name], [name] or [name] at their History and Physical visit prior to elective anterior cervical spine surgery in a private room at the Spine Center. 2. Subjects will be told about the study at this visit, all questions will be answered by the surgeons and the research coordinator, all surveys that need to be completed will be shown to the potential subjects and they will be given the opportunity to consent. 3. If consented, the subject will be asked to complete baseline surveys (Bazaz, EAT-10 and Dysphagia Short Questionnaire) at this visit. 4. The subject will be randomized to receive either single dose steroid (dexamethasone) or saline (placebo) prior to surgery. 5. The subject will be seen post-op day one by the research coordinator (and post op Day 2 if the subject is still hospitalized) who will administer the surveys in the hospital room. 6. Following Day one surveys, and after discharge, the subject will be called from a private room of a research coordinator to complete the answers to the surveys via phone call at Day 2, Week 1, Week 2, Month 1, Month 3, Month 6 and Month 7. If the subject is in the clinic for follow up at the designated time frame for survey administration, the surveys will be completed in a private room in the clinic.

Does this study have a Federal Certificate of Confidentiality? If yes, attach the certificate on the Notes & Attachments page.

No

### **Financial Considerations**

Will the subjects incur any costs to participate in this project (e.g., travel, physician fees, study procedures, study drugs)?

No

Will the subject be paid (money, gift certificates, coupons, etc.) to participate in this research project?

No

Will WVU students receive extra credit for participating in this research project?

No

### **Advertisements**

Will there be advertisements for this study?

No

### **Drug/Substance/Nutrient/Biologic**

Are there any drugs/substances/nutrients/biologics being used in this research study for investigational/research purposes ONLY?

Yes

Enter the name of the first drug being used for investigational/research purposes ONLY.

dexamethasone

Is this an Investigational New Drug (IND) (if so, please attach the investigator brochure or applicable documentation)?

No

Is this drug/substance/nutrient/biologic being used off-label (if so, please attach the package insert or applicable documentation)?

No

Does this drug/substance/nutrient/biologic meet the requirements of an IND exemption? The clinical investigation of a marketed drug or biologic does not require submission of an IND if all six (6) exemption conditions are met.

No

Is there a second drug/substance/nutrient/biologic used in this research study for investigational/research purposes ONLY?

No

Provide any other information regarding the drugs/substances/nutrients/biologics being used in this study that is relevant to the IRB review.

Dexamethasone is a commonly used drug administered by anesthesiologists when patients are having difficulty swallowing after surgery or to reduce nausea and vomiting.

Will all drugs/substances/nutrients/biologics being used in this study be provided free of charge?

Yes

Will all drugs/substances/nutrients/biologics being used in this study be stored at the WVU Healthcare Pharmacy (WVUHP)? All drug storage must be approved by the WVUHP.

Yes

Will there be any drugs/substances/nutrients/biologics used in this study NOT for investigational/research purposes?

No

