**Design**

Please provide a lay summary (written at 6th grade level) that includes a statement about the purpose and the general aims of the research.

Dysphagia (difficulty swallowing) is common following anterior cervical spine surgery. Studies have documented persistent swallowing difficulty up to two years postoperatively. The long term objective is to change the treatment paradigm for cervical spine surgery to minimize dysphagia and associated complications. The specific aims are to identify the effect of a single dose of perioperative steroid on dysphagia and to develop a treatment protocol for the frequency of perioperative steroids needed to reduce dysphagia. This is a prospective, randomized, placebo-controlled study. Patients will be given a single dose of dexamethasone or normal saline intratoperatively and then assessed at multiple time points up to one year. The research question is what is the effect of a single dose of perioperative steroid on dysphagia after anterior cervical spine surgery? The survey instruments used to determine difficulty swallowing include the Bazaz, Dysphagia Short Questionnaire, and EAT 10. To administer the Bazaz instrument, the study coordinator will ask the subject if he/she has difficulty swallowing liquid food and give the options 'none', 'rare', 'present all the time'. The options for solid food are 'none', 'rare', 'occasional only with specific foods', or 'frequent majority of solids'. The options on the left side of the questionnaire determine the level of difficulty. If a subject has no difficulty swallowing both liquid and solid food, 'none' will be chosen. The level of difficulty swallowing is determined by the highest difficulty, e.g. if a subject had no difficulty swallowing liquid food and has rare difficulty swallowing solid food, 'mild' will be chosen. If the subject has no difficulty swallowing liquid food but has frequent difficulty swallowing solid food, 'severe' will be chosen.

Fully describe all procedures to be performed, from start to finish, numbering your procedures 1,2,3 or A, B, C (e.g., 1. Recruiting, 2. Consent, 3. Collecting data, 4. How findings will be shared, etc.).

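### The plan sets no limit on open-label dexamethasone, which anesthesiologists commonly give, so control patients may receive the trial drug and the arms may be pulled together

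*Combined protocol and SAP*

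**What the plan says.** All references are to the combined protocol and SAP.

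- **Drug/Substance/Nutrient/Biologic.** On information relevant to the ethics review, the answer includes: "Dexamethasone is a commonly used drug administered by anesthesiologists when patients are having difficulty swallowing after surgery or to reduce nausea and vomiting". One of those two uses, swallowing difficulty, is what the trial measures.
- **Design, procedures, step 6.** After the antibiotics, "the single dose of steroid or saline will be given by the anesthesia team, who are blinded to the group assignment". The step says nothing about other dexamethasone or other steroids. The prompt for this list reads "Fully describe all procedures to be performed, from start to finish".
- **Design, standard of care procedures.** The answer is "Everything outside of the randomization".
- **Subjects, exclusion criteria.** The only steroid restriction is the exclusion of "patients on chronic steroids". That governs entry, not care around the operation.
- **Design, lay summary and data analysis.** One aim is "to develop a treatment protocol for the frequency of perioperative steroids needed to reduce dysphagia", and the analysis plan includes a comparison with the institution's previous three-dose study. Power rests on dysphagia at two weeks, 50% against 20%, with 32 patients per arm and 81% power. The total is 80 after allowing for 20% dropout.

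The supplied text describes no recording of non-study steroid doses. The data-capture fields, the Data Safety Monitoring Plan and the scientific rationale were not supplied and may cover this.

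**The concern.** The trial asks what one dose of dexamethasone does compared with none. The plan followed as written lets a control patient receive dexamethasone for nausea in the operating room, or afterwards for nausea or swallowing difficulty. Nobody would have departed from the protocol.

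Blinding stops clinicians from choosing by known arm, but it does not prevent dilution. If a further dose adds little for patients who have already had the study dose, equal use in both arms still moves controls towards the treated group. Use for swallowing difficulty need not be equal: clinicians responding to symptoms will treat more often in whichever arm has more of them, and if the drug works that is the control arm.

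Two consequences follow. A small observed difference could mean a weak drug effect or a diluted contrast, and without doses tabulated by arm the two could not be told apart. Unrecorded extra doses would also blur the aim about dosing frequency and the comparison of one dose with three. Charts can show later who received what, but contrast lost at surgery cannot be recovered.

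**Working it through.** **Inputs from the plan (Design, data analysis):** control rate 0.50, steroid rate 0.20, 32 per arm, significance level 0.05 with sidedness not stated, stated power 81%.

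**Assumed, because the documents give no figure:** c, the share of patients given a non-study dose (10%, 20% or 30%), and f, its effect as a fraction of the study dose (1 or 0.5).

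**Power formula** (pooled-variance normal approximation, p̄ the mean of p1 and p2, Δ = p1 − p2):

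power = Φ{ [Δ√n − z√(2p̄(1−p̄))] / √(p1(1−p1) + p2(1−p2)) }

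**Step 1: the plan's own figure.** With one-sided 0.05, z = 1.645 and p̄ = 0.35:
(0.30 × √32 − 1.645 × 0.6745) / 0.6403 = (1.6971 − 1.1095) / 0.6403 = 0.918, so power = 0.821. This is close to the stated 81%; two-sided 0.05 gives 0.721. The one-sided basis is used below only because it approximately matches the plan. Sidedness is not part of this point.

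**Step 2: a further dose adds nothing in the steroid arm.** The control rate becomes 0.50 − 0.30cf; the steroid rate stays at 0.20. For c = 0.20 and f = 1, the control rate is 0.44, Δ = 0.24 and p̄ = 0.32:
(0.24 × √32 − 1.645 × 0.6597) / 0.6375 = (1.3576 − 1.0851) / 0.6375 = 0.4275, so power = 0.6655, or 67%.

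**Step 3: a further dose has the same relative effect in both arms.** The study dose multiplies risk by 0.20/0.50 = 0.40. If a further dose does the same, each arm's rate is multiplied by 1 − 0.60c. For c = 0.20 the factor is 0.88, the rates are 0.44 and 0.176, Δ = 0.264 and p̄ = 0.308:
(0.264 × √32 − 1.645 × 0.6529) / 0.6256 = (1.4934 − 1.0739) / 0.6256 = 0.6705, so power = 0.749, or 75%.

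**Step 4: the range.**

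| Assumption | c | Contrast (points) | Power at 32 per arm | n per arm for 80% |
|---|---|---|---|---|
| No non-study use | 0 | 30 | 82% | 31 |
| Full effect, nothing added in steroid arm | 10% | 27 | 75% | 37 |
| | 20% | 24 | 67% | 46 |
| | 30% | 21 | 57% | 59 |
| Half effect, nothing added in steroid arm | 10% | 28.5 | 79% | 34 |
| | 20% | 27 | 75% | 37 |
| | 30% | 25.5 | 71% | 41 |
| Same relative effect in both arms | 20% | 26.4 | 75% | 37 |

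The plan enrols 40 per arm and expects 32 after dropout.

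**Step 5: unequal use.** If 20% of controls and no steroid-arm patients receive a fully effective non-study dose, the rates are again 0.44 and 0.20. That is the Step 2 case, with power 67%. For a control share of 20%, lower use in the steroid arm therefore falls between the Step 3 and Step 2 results.

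**The case against.** **Use may be rare or already counted.** The sentence about anesthesiologists describes general familiarity with the drug. It gives no rate, dose or timing for trial patients, so it does not show that such doses are expected. The 50% control rate comes from a literature review and may already include similar use, in which case there is no loss. This stands, and it is why the figures are an illustration.

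**The model can overstate the loss.** Full effect equates a dose of unknown size with 0.3 mg/kg. Assuming no added benefit in the steroid arm sits uneasily with the promising multi-dose results cited under Potential Benefits. This also stands; with the same relative effect in both arms the 20% case is 75%, not 67%.

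**The comparison stays valid.** Background use alike in both arms does not raise the false-positive rate, and dexamethasone added to usual care is a legitimate question. True, but the stated question concerns a single dose, and the aims and the three-dose comparison depend on how many doses patients received.

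**An attachment may contain a rule.** Possible. The procedure list, where the anesthesia team would look, contains none.

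**A stronger reading: the plan contradicts itself.** Dexamethasone is the answer to "Enter the name of the first drug being used for investigational/research purposes ONLY", and the answer to "Will there be any drugs/substances/nutrients/biologics used in this study NOT for investigational/research purposes" is No. A reader might infer that clinical dexamethasone is thereby excluded, in conflict with leaving other care as usual. The documents do not support that. Step 6 itself has antibiotics given in the operating room, plainly not for research, and the answer is still No. The item evidently covers drugs supplied under the study; its neighbours ask about free provision and pharmacy storage. Read that way, it is consistent with the standard-of-care statement and says nothing either way about clinical dexamethasone.

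**Conclusion.** The point holds as a gap in trial conduct. By the plan's own account the trial drug is in common use by the team that delivers the study dose, and nothing in the supplied text keeps it from control patients. Any such use would tend to pull the arms together.

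The size is unknown. Use in 10% to 30% of patients, at full effect and with nothing added in the steroid arm, would take power from 82% to between 75% and 57%; milder assumptions give smaller losses. The loss is zero if no such doses are given or if the 50% rate already reflects them. A reader might infer that the trial's power really is 67%, or that crossover is expected. The documents support neither, since both the rate and the effect of non-study doses are assumptions here. No internal contradiction is claimed.

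The change is worth making before further patients have surgery. Confidence is medium, because of the attachments not seen and the unknown rate of use.

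**What to change.** 1. Add to step 6 that the anesthesia team gives no open-label dexamethasone to prevent or treat nausea in either arm, and uses a non-steroid antiemetic instead. Treatment of swallowing or airway problems stays at clinical discretion.
2. Record every in-hospital non-study systemic steroid dose, for any indication, from the anesthesia and medication records: drug, dose, date and indication.
3. Report these doses by arm, and next to the three-dose comparison.
4. Keep the as-randomised analysis of observed survey scores as the main one, with no imputation over scores that were observed.

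The restriction closes the nausea route only. Use for swallowing difficulty cannot reasonably be barred, so recording makes it visible without preventing it.

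Cost: a sentence or two in step 6, a few data fields for 80 patients, and the anesthesia team's agreement to a small departure from usual antiemetic practice. The sample size does not change.
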